7.2.1. Adverse Events

7.2.1.1. Definition of Adverse Events

An AE is defined as any untoward medical occurrence associated with the use of a drug in humans, whether or not considered drug related. An AE can therefore be any unfavorable and unintended sign, symptom, or disease temporally associated with the use of an investigational product, whether or not thought to be related to the investigational product. An AE may also constitute complications occurring as a result of protocol-mandated interventions (eg, invasive procedures such as biopsies), including the period prior to receiving the first dose of the study drug (eg, medication wash out, biopsies). In addition to new events, any increase in the severity or frequency of a pre-existing condition that occurs after the participant signs the ICF is considered an AE. This includes any side effect, injury, toxicity, or sensitivity reaction.

A suspected adverse reaction is any AE for which there is a reasonable possibility that the drug caused the AE. For the purposes of expedited safety reporting, "Reasonable possibility" means there is evidence to suggest a causal relationship between the drug and the AE. Suspected adverse reaction implies a lesser degree of certainty about causality than adverse reaction, which means any AE caused by a drug.

Life-threatening AE or life-threatening suspected adverse reaction is an AE or suspected adverse reaction that, in the view of either the investigator or Pfizer, places the study participant at immediate risk of death. It does not include an AE or suspected adverse reaction that, had it occurred in a more severe form, might have caused death.

An AE or suspected adverse reaction is considered "unexpected" if it is not listed in the current IB or is not listed at the specificity or severity that has been observed.

An SAE or serious suspected adverse reaction is an AE or suspected adverse reaction that at any dose, in the view of the either the investigator or Pfizer, results in any of the following outcomes:

- Death
- A life-threatening AE
- Inpatient hospitalization or prolongation of existing hospitalization
- Persistent or significant incapacity or disability (substantial disruption of the ability to conduct normal life functions)
- A congenital anomaly/birth defect
- Important medical events (IME) that may not result in death, be immediately lifethreatening, or require hospitalization may be considered serious when based upon medical judgement, they may jeopardize the study participant and may require medical or surgical intervention to prevent one of the outcomes listed in this definition

NOTE: Hospitalization planned prior to study enrollment (eg, for elective surgeries) are not considered SAEs. Hospitalizations that occur for pre-existing conditions that are scheduled after study enrollment are considered SAEs.

The Investigator will assess each AE for seriousness, severity, and relationship to investigational product.

7.2.1.2. Severity of Adverse Events

Whenever possible, the severity of all AEs will be graded using the National Cancer Institute's Common Terminology Criteria for Adverse Events (NCI CTCAE), Version 4.03.

For AEs not adequately addressed in the NCI CTCAE Version 4.03, the following criteria should be used (Table 7).

Table 7. Grading for Adverse Events Not Covered in the NCI CTCAE

Severity	Description
Grade 1 – Mild	Asymptomatic or mild symptoms; clinical or diagnostic observations only; intervention not indicated
Grade 2 – Moderate	Minimal, local or non-invasive intervention indicated; limited age appropriate instrumental activities of daily living (ADL)
Grade 3 – Severe	Medically significant but not immediately life threatening; hospitalization or prolongation of hospitalization indicated; disabling; limiting self-care ADL.
Grade 4 – Life threatening	Life threatening consequences; urgent intervention indicated

Table 7. Grading for Adverse Events Not Covered in the NCI CTCAE

Severity	Description
Grade 5 – Fatal	Death

Abbreviations: NCI CTCAE = National Cancer Institute Common Terminology Criteria for Adverse Events.

To make sure there is no confusion or misunderstanding between the terms "serious" and "severe", which a not synonymous, the following note of clarification is provided. The term "severe" is often used to describe the intensity (severity) of a specific event (i.e. mild, moderate, or severe); the event itself, however, may be of relatively minor medical significance (eg, severe headache). This is not the same as "serious" which is based on the study participant / event outcome or action criteria associated with events that post a threat to a participant's life or functioning. Seriousness (not severity) serves as a guide for defining regulatory reporting obligations.

7.2.1.3. Relationship to Investigational Product

The relationship of an AE to the investigational product should be determined by the Investigator according to the following definitions:

- NOT RELATED: Evidence exists that the AE has an etiology other than the study drug and/or the temporal relationship of the AE/SAE to the investigational product administration makes the relationship unlikely. If an SAE is not considered related to study drug, then an alternative explanation should be provided.
- RELATED: A temporal relationship exists between the event onset and the
 administration of the study drug makes a causal relationship possible or probably.
 It cannot be readily explained by the participant's clinical state or concomitant
 therapies and may appear, with some degree of certainty, to be related based on
 the known therapeutic and pharmacologic actions of the drug. Good clinical
 judgement should be used for determining causal assessment.

7.2.1.4. Unexpected Adverse Reactions

An adverse event is 'unexpected' if its nature and severity are not consistent with the information about the study drug provided in the Reference Safety Information (RSI) in the voxelotor IB.

7.2.2. Adverse Event Reporting

7.2.2.1. General

For study participants transitioning from the primary study (GBT440-031), all AEs (both serious and nonserious) will be recorded from the time both informed consent is obtained for this extension study and End of Treatment (EoT) visit has been completed in the primary study (GBT440-031) until 28 days after last dose of study drug or End of Study visit in this study.

Before EoT visit is completed in the primary study (GBT440-031), study sites must continue to collect and report to Pfizer Safety, SAE through and including 28 calendar days after the last dose of the investigational product (IP) or EoT visit, in the primary study, even though the patient may have signed the informed consent (IC) or signed the IC and taken the first dose on the rollover study GBT440-034/C5341022. Study recording of adverse events in the case report form (CRF) must continue in the primary study until EoT visit is achieved.

Adverse events reported as ongoing at the completion of GBT440-031, will be recorded in the Medical History CRF in this study.

After End of Treatment visit in the study GBT440-031, reporting of all AEs and SAEs in the study GBT440-034/C5341022, must be promptly documented on the AE CRF via the EDC system. Requirements for immediate safety reporting will follow standard process as specified in section 7.2.3.

The investigator is responsible for evaluating all AEs, obtaining supporting documents, and ensuring documentation of the event is complete. Details of each reported AE must include at minimum severity, relationship to study drug, duration and outcome. All (both serious and nonserious) AEs must be followed until they are resolved or stabilized, or until reasonable attempts to determine resolution of the event are exhausted.

When a clinically important AE remains ongoing at the end of the active collection period, follow-up by the investigator continues until the AE or SAE or its sequelae resolve or stabilize at a level acceptable to the investigator and Pfizer concurs with that assessment.

For participants who are screen failures, the active collection period ends when screen failure status is determined.

If the participant withdraws from the study and also withdraws consent for the collection of future information, the active collection period ends when consent is withdrawn.

If a participant permanently discontinues or temporarily discontinues study intervention because of an AE or SAE, the AE or SAE must be recorded on the CRF and the SAE reported using PSSA. The Sponsor/Medical Monitor(s) must be notified of the study participant discontinuation.

Investigators are not obligated to actively seek information on AEs or SAEs after the participant has concluded study participation. However, if the investigator learns of any SAE, including a death, at any time after a participant has concluded study participation, and they consider the event to be reasonably related to the study intervention, the investigator must promptly report the SAE to Pfizer using PSSA.

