7.2. Adverse and Serious Adverse Events

Safety assessments will consist of recording all AEs and SAEs, protocol-specified hematology and clinical chemistry variables, clinical examination findings, measurement of protocol-specified vital signs, and the results from other protocol-specified tests that are deemed critical to the safety evaluation of voxelotor.

All AEs will be recorded from the time the study participant signs the ICF until at least 28 days after last dose of study drug or EOS visit (per Appendix 1). The determination, evaluation, reporting, and follow-up of AEs will be performed as outlined in this section. At each visit, the study participant will be asked about any new or ongoing AE since the previous visit. Assessments of AEs will occur at each study visit.

Clinically significant changes from study baseline in physical examination findings, weight, vital signs, and clinical laboratory parameters, will be recorded as AEs or SAEs, as appropriate.

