### Treatment-Emergent Adverse Event

Treatment-emergent adverse events (TEAEs) are defined as adverse events with onset on or after the date of informed consent until 28 days after last dose of study drug. Note: For this study, informed consent date is used (rather than first dose date) as the majority of participants were previously treated with voxelotor in the parent study GBT440-031.

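### Adverse events starting between OLE consent and the parent-study End of Treatment visit are TEAEs under the SAP but sit on the GBT440-031 CRF, and the SAP has no rule to bring them in

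*Protocol*

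**What the plan says.** **Protocol 7.2.2.1** sets two conditions for recording adverse events in GBT440-034: events are recorded "from the time both informed consent is obtained for this extension study and End of Treatment (EoT) visit has been completed" in the parent study. It foresees an overlap. Sites keep reporting serious events under the parent study "even though the patient may have signed the informed consent (IC) or signed the IC and taken the first dose on the rollover study". The CRF rule is explicit: "Study recording of adverse events in the case report form (CRF) must continue in the primary study until EoT visit is achieved". Only afterwards does the GBT440-034 form take over: "After End of Treatment visit in the study GBT440-031, reporting of all AEs and SAEs in the study GBT440-034/C5341022, must be promptly documented". For events that have not ended: "Adverse events reported as ongoing at the completion of GBT440-031, will be recorded in the Medical History CRF in this study". Protocol 7.1.1 repeats that last rule.

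**Protocol 7.2** gives a different start: "All AEs will be recorded from the time the study participant signs the ICF until at least 28 days after last dose". It sets no EoT condition and names no CRF.

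**SAP 3.1**, repeated in 5.3.2, defines TEAEs as "adverse events with onset on or after the date of informed consent until 28 days after last dose of study drug". Its stated reason for starting at consent is that most participants had already received voxelotor in the parent study. Protocol 8.1.1.1 instead starts at initiation of study drug. SAP 3.1 also brings parent-study Week 72, EoT and End of Study values into the baseline. It has no equivalent provision for parent-study adverse events.

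**The concern.** The analysis window and the data collection open on different dates. Where the parent EoT visit falls after OLE consent, the SAP claims events for GBT440-034 that the protocol has placed in another study's database.

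The days that matter most are those between the first OLE dose and the EoT visit. SAP 2.1 says all participants receive 1500 mg. For a prior-placebo participant these days are the first exposure to voxelotor, and for a prior-900 mg participant the first exposure at the higher dose. The protocol itself gives these participants extra visits at Weeks 4 and 8. Safety is the first-listed endpoint. If early events are left out, the tables understate the period in which new-exposure events would be expected to appear.

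**Working it through.** No figure in the plan depends on this point, so there is none to reproduce. The check is to trace an event by its onset date.

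**1. Dates.** Let C be OLE consent, D the first OLE dose and E the parent EoT visit. The SAP window opens at C. Recording in GBT440-034 opens at the later of C and E. The gap is max(0, E − C) days, so it is zero if E falls on or before C.

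**2. Where an event goes when C comes before E.**

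| Onset | CRF (protocol 7.2.2.1) | TEAE under SAP 3.1 | TEAE under protocol 8.1.1.1 |
|---|---|---|---|
| From C, before D and before E | GBT440-031 | Yes | No, before OLE drug |
| From D, before E | GBT440-031 | Yes | Yes, if new or worsened |
| From E onward | GBT440-034 | Yes, to 28 days after last dose | Yes, once dosed |

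The middle row is treatment-emergent under both definitions and still lies outside the GBT440-034 adverse event data. The first row matters only because the SAP chose consent as its start.

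**3. Whether anything brings the event back.** An event that resolves before E stays on the parent CRF. One still ongoing at completion of GBT440-031 arrives as Medical History. Under protocol 7.2.2.4 it becomes an adverse event again only if it increases in frequency or severity or its character worsens. SAP section 2 lets the SAP supersede the protocol's analysis methods, but a wider window does not supply records held elsewhere.

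**4. Outputs affected.** These are the TEAE and serious TEAE tables in SAP 5.3.2 and the SCD-complication incidence and rates in 5.4.1, which are built on TEAEs. Study Year is also counted from consent, so for gaps shorter than a year the whole loss falls in Study Year 1 of the by-year tables. The denominators do not shrink to match: exposure in 5.3.1 runs from the first OLE dose, and 5.4.1 does not tie the start of assessment time to the parent EoT visit. Rates are biased low if that time starts at consent or first dose.

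**5. Scale, for illustration only.** The gap g is an assumption; the documents give none. N = 274 is the SAP 2.3 maximum, and 365.25 is the SAP's year length. Share of Study Year 1 for one affected participant = g / 365.25. Upper limit if every participant were affected = 274 × g / 365.25 person-years.

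| g (days) | Share of Study Year 1 | Upper limit, person-years |
|---|---|---|
| 0 | 0% | 0 |
| 1 | 0.3% | 0.75 |
| 7 | 1.9% | 5.25 |
| 14 | 3.8% | 10.5 |
| 28 | 7.7% | 21.0 |

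Over long follow-up the share is small: 14 days of the 1,344 days to Week 192 is 14 / 1344 = 1.0%. Any effect is therefore on early-exposure summaries far more than on whole-study totals.

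**The case against.** The strongest reply is that the loss is inferred from silence. The SAP definition rests on onset date and names no database, and the table specifications are in a separate document, so programmers may already merge the two studies. That is fair: the events are missed only if GBT440-034 data are used alone. But that is the natural reading of a SAP that names the parent-study values it imports and does not mention adverse events.

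Second, nobody may be affected. The baseline rule expects parent-study final values on or before the first OLE dose, which suggests that the EoT visit usually came first. This limits the first-dose-to-EoT part. It does not exclude consent before the EoT visit, which is where the SAP window opens.

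Third, timing. The summary of changes lists 7.2.2.1 as revised for the move to the new sponsor's safety systems, and this amendment is dated December 2023, when Table 1 already listed GBT440-031 enrollment as complete. The wording may post-date most rollovers, and the rule then in force cannot be seen. This stands: the existence of a rule is weak evidence that overlaps occurred, and changing CRF ownership now would probably alter no collected data. The remedy belongs in the SAP.

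A reader might infer three stronger things that the documents do not support:

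- That protocol 7.2 and 7.2.2.1 say opposite things. They differ in start point, but 7.2 names no CRF and can be read as the general rule beside a specific one.
- That lost events in former placebo participants would be counted under placebo. That depends on the parent study's analysis plan, which is not available.
- That serious events go unreported. They still reach the sponsor's safety group; the issue is where they are analyzed.

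**Conclusion.** The point holds as a gap between stated rules. Followed as written, 7.2.2.1 places events with onset between OLE consent and the parent EoT visit outside the GBT440-034 adverse event data, while SAP 3.1 and 5.3.2 count them as TEAEs and provide no way to obtain them. The bias in TEAE, serious event and TEAE-based SCD-complication counts can only be downward, and it bears mainly on early exposure in prior-placebo and prior-900 mg participants.

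Its size is unknown. The documents give neither how many participants had an overlap nor how long it lasted, and the number may be zero. A reader might take all prior-placebo participants as affected, but nothing in the documents shows that any of them had an overlap. The conclusion assumes that the analysis uses GBT440-034 adverse event records only. The study is descriptive, so no test or power statement is touched. The point is worth correcting because one date comparison settles whether it matters.

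**What to change.** In SAP 3.1, 5.3.2 and 5.4.1:

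1. Identify by a date check every participant whose parent EoT visit falls after OLE consent, and report the number and the length of the overlap. If there are none, say so in the study report.
2. Add to the TEAE dataset every GBT440-031 adverse event or serious adverse event record with onset on or after OLE consent, flagging those on or after the first OLE dose. Merging only from first dose would leave part of the SAP's own window uncovered.
3. Do not treat the matching GBT440-034 Medical History entries as pre-existing conditions, and de-duplicate serious events reported under both studies.

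Alternatively, start the TEAE window and its person-time at the later of OLE consent and the parent EoT visit, and list the overlap events separately. Numerator and denominator then match, at the price of leaving the overlap events out of the main tables.

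In either case, reconcile the start of adverse event recording in protocol 7.2 with 7.2.2.1.

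The cost is a few SAP sentences and a small merge of two sponsor-held databases, with recoding to the MedDRA version used for the analysis. No new data are needed. TEAE counts may rise slightly.

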7.2.2.2. Diagnosis Versus Signs and Symptoms

If known, a diagnosis should be recorded on the CRF rather than individual signs and symptoms (eg, record only liver failure or hepatitis rather than jaundice, asterixis, and elevated transaminases). However, if a constellation of signs and/or symptoms cannot be

medically characterized as a single diagnosis or syndrome at the time of reporting, each individual event should be recorded separately on the CRF. If a diagnosis is subsequently established, it should be reported as follow-up information.

7.2.2.3. Abnormal Laboratory Values

Only clinically significant laboratory abnormalities as assessed by the Investigator will be recorded on the AE CRF (eg, abnormalities that have clinical sequelae, require study drug dose modification, etc.). If the clinically significant laboratory abnormality is a sign of a disease or syndrome (eg, ALK and bilirubin 5x ULN associated with cholecystitis), only the diagnosis (eg, cholecystitis) should be recorded as an AE on the CRF.

If the clinically significant laboratory abnormality is not a sign of a disease or syndrome, the abnormality itself, characterized by precise clinical term, as possible, should be recorded on the CRF (eg, elevated potassium of 7.0 mEq/L should be recorded as 'hyperkalemia').

Observations of the same clinically significant laboratory abnormality from visit to visit should not be repeatedly recorded on the AE CRF, unless their severity, seriousness, or etiology changes.

Note: Potential drug-induced liver injury (DILI; Hy's law) cases are to be reported as SAEs (Section 7.2.3). For suggested actions and follow-up assessments in the event of potential DILI, refer to Appendix 2. (This note is included to support Study transition to Pfizer Pharmacovigilance processes and systems.)

7.2.2.4. Preexisting Medical Conditions

A preexisting medical condition is one that is present at the start of the study. Such conditions should be recorded on the Medical History and Baseline Conditions CRF.

If a preexisting medical condition increases in frequency or severity, or if the character of the condition worsens during the study, the condition should be recorded as an AE or SAE. When recording such events on the AE CRF, it is important to convey the concept that the preexisting condition has changed by including applicable descriptors (eg, "more frequent headaches").

7.2.2.5. Worsening of Sickle Cell Disease

Complications and symptoms of SCD should be recorded as an AE or SAE if judged by the Investigator to have worsened in severity and/or frequency or changed in nature during the study.

7.2.3. Serious Adverse Events, Serious Adverse Drug Reactions, and Requirements for Immediate Reporting

All SAEs, regardless of causal attribution, occurring on this study will be recorted on the AE eCRF and reported to Pfizer Safety via PSSA within 24 hours of the Investigator, designee, or site personnel's knowledge of the event. In the event that the EDC system is not available, paper SAE report forms will be used to report the SAE and faxed or emailed to Pfizer Safety.

The information reported on the paper SAE report form should be entered into PSSA once available.

The Sponsor may request additional information pertaining to the SAE from the investigational site. Follow-up reports must be submitted within 24 hours of awareness as additional information becomes available.

All SAEs regardless of causal attribution must be followed to resolution, stabilization or until reasonable attempts to determine resolution of the SAE are performed.

7.2.3.1. Reporting Suspected Unexpected Serious Adverse Reactions (SUSARs) and Urgent Safety Issues

The Sponsor is responsible for reporting Suspected Unexpected Serious Adverse Reactions (SUSARs) to regulatory agencies, competent authorities, IRBs/ECs, and Investigators, as per local laws and regulations. Fatal and life-threatening SUSARs will be submitted no later than 7-calendar days of first knowledge of the event and follow-up information submitted within an additional 8 calendar days, or as otherwise required per local laws and regulations. All other SUSARs will be submitted within 15-calendar days of first knowledge of the event. The Investigator is responsible for notifying the local IRB or local ECs of all SAEs that occur at his or her site as required by local regulations or IRB/EC policies, if this responsibility resides with the site.

Investigators are required to report any urgent safety matters to the Sponsor within 24 hours. The Sponsor will inform regulatory authorities, IRBs/ECs, and Investigators of any events (eg, change to the safety profile of voxelotor, major safety findings that may place study participants at risk) that may occur during the clinical trial that do not fall within the definition of a SUSAR but may adversely affect the safety of study participants, as required, in accordance with applicable local laws and regulations. The reporting period for urgent safety issues is the period from signing the informed consent until 28 days after last dose of study drug or EOS visit on GBT440-034/C5341022.

